2 INTRODUCTION

The purpose of this prospective, non-randomized, multi-center observational study is to observe the safety and effectiveness of the WATCHMAN FLXTM Left Atrial Appendage Closure (LAAC) Device for subjects with non-valvular atrial fibrillation to reduce the risk of stroke in Hong Kong area. The data collected in this study may also be used for product registration in other areas to show that ethnic difference might not play an important role in the performance of WATCHMAN FLXTM.

This statistical analysis plan addresses the planned analyses for the Hong Kong WATCHMAN FLX Clinical trial based on the protocol version Dated July 19, 2021.

3 ENDPOINT ANALYSIS

3.1 Primary Endpoint

The Primary effective endpoint is the occurrence of non-effective LAA closure defined as any peri-device flow > 5mm demonstrated by TEE/CT/MRI at First Follow-up. The Primary safety endpoint is the occurrence of one of the following events between the time of implant and within 7 days following the procedure or by hospital discharge, whichever is later: all-cause death, ischemic stroke, systemic embolism, or device or procedure related events requiring open cardiac surgery or major endovascular intervention such as pseudoaneurysm repair, AV fistula repair, or other major endovascular repair. Percutaneous catheter drainage of pericardial effusions, snaring of an embolized device, thrombin injection to treat femoral pseudoaneurysm and nonsurgical treatments of access site complications are excluded from this endpoint.

No formal hypothesis will be tested for the primary endpoint. So, no formal sample size calculation is performed based on the primary endpoint. The following table provides a 95% confidence interval (exact methods) for a sample size of 50 if there are $0 \sim 5$ events.

| Events | Rates (n=50) | Lower 95%CI | Upper 95%CI |
|--------|--------------|-------------|-------------|
| 0 | 0% | 0.0% | 7.1% |
| 1 | 2% | 0.1% | 10.6% |
| 2 | 4% | 0.5% | 13.7% |
| 3 | 6% | 1.3% | 16.5% |
| 4 | 8% | 2.2% | 19.2% |
| 5 | 10% | 3.3% | 21.8% |

3.2 Secondary Endpoints

The secondary endpoint is the occurrence of ischemic stroke or systemic embolism at 12 months from the time of implant.

3.3 Additional Analysis

The occurrence of stroke (including ischemic and/or hemorrhagic), cardiovascular death (cardiovascular and/or unexplained cause) and systemic embolism.

3.4 Statistical Methods

No formal hypothesis will be tested for this small observational study. Data and outcome variables collected at baseline, procedure and post procedure follow up will be summarized using descriptive statistics.

For continuous variables, the mean, standard deviation, median, interquartile range (IQR), range, and 95% confidence intervals will be reported. Confidence intervals (95%) for the difference between means will be used to compare groups. For proportions, percentage, count/sample, and 95% confidence intervals will be reported. For time-to-event analyses, all patients not having an event or who are lost to follow-up will be censored at the time of the last documented follow-up visit.

3.5 Endpoints Analysis Included in the Clinical Study Report

For the primary endpoint report (30-100 days post procedure), below endpoint assessments will be included:

- Primary effectiveness endpoint, which refers to the occurrence of non-effective LAA closure at first 30-100 days follow-up.
- Primary safety endpoint, which refers to the occurrence of the primary safety endpoint events between the time of implant and within 7 days following the procedure or by hospital discharge (whichever is later).
- Additional endpoints and other major clinical events, including the occurrence of below events at 30-100 days follow-up:
 - stroke, including ischemic and/or hemorrhagic
 - TIA
 - cardiovascular death, including cardiovascular and/or unexplained cause
 - systemic embolism
 - device embolization
 - device thrombus
 - serious pericardial effusion
 - major bleeding

For the 12-month report, below endpoint assessments will be included:

- Primary effectiveness endpoint, which refers to the occurrence of non-effective LAA closure at 30-100 days follow-up.
- Primary safety endpoint, which refers to the occurrence of the primary safety endpoint events between the time of implant and within 7 days following the procedure or by hospital discharge (whichever is later).
- Secondary endpoint, which refers to the occurrence of ischemic stroke or systemic embolism at 12-month follow-up.
- Additional endpoints and other major clinical events, including the occurrence of below events at 12-month follow-up:

Form/Template 90702621 Rev/Ver AF, Boston Scientific WATCHMAN FLX™ HK Study, SAP, 92820808, Rev/Ver AA Page 9 of 14

- stroke, including ischemic and/or hemorrhagic
- TIA
- cardiovascular death, including cardiovascular and/or unexplained cause
- systemic embolism
- device embolization
- device thrombus
- serious pericardial effusion
- major bleeding

4 GENERAL STATISTICAL METHODS

4.1 Analysis Sets

Roll-in subjects are excluded from all primary and secondary endpoints analyses and will be treated separately.

The primary analysis set for the primary effectiveness analysis will be the "per-protocol" analysis set, including implanted subjects with a completed first follow-up visit. The primary analysis set for the primary safety analysis will be the "intent-to-treat" analysis set, including implanted or attempted subjects. It is estimated that both primary effectiveness analysis and primary safety analysis dataset will include at least 40 subjects. For secondary endpoint and additional analysis, different datasets could be used exploratively.

The definitions on the different subject status and classification are provided as below:

Consent Ineligible: A subject who has signed informed consent but is found to not meet eligibility criteria will be classified as "**Consent Ineligible**". There are no FU or adverse event reporting requirements for consent ineligible subjects. Subjects determined to be Consent Ineligible do not count towards the enrollment ceiling and will not be used for analysis of the endpoints.

Intent: A subject who signs informed consent, meets eligibility criteria, but then does not undergo an implant of a WATCHMAN FLX device will be classified as "**Intent**". There are no FU or adverse event reporting or primary endpoint analysis requirements for Intent subjects. Intent subjects do not count towards the enrollment ceiling and will not be used for analysis of the endpoints.

Attempt: A subject who signs informed consent, meets eligibility criteria and has had the WATCHMAN FLX Access Sheath inserted to implant the device, but eventually does not receive a WATCHMAN FLX device will be classified as "**Attempt**". There are no FU requirements for Attempt subjects; however, adverse events will be collected up to the point of subject withdrawal. Attempt subjects count towards the enrollment ceiling and will be used for analyses of the endpoints.

Implant: A subject who is successfully implanted with the WATCHMAN FLX device will be classified as "**Implant**". These subjects are followed in accordance with the FU schedule and included in all study analyses.

Roll-in and non-roll-in: Each site might have up to 2 roll-in subjects if the site has never implanted a WATCHMAN FLX before. Roll-in subjects should be decided before the implant procedure and might be classified as Attempt or Implant after the procedure. Roll-in subjects are enrolled and counted to the ceiling of the sample size. Other enrolled subjects are defined as non-roll-in.

4.2 Statistical Methods

Data and outcome variables will be summarized using descriptive statistics for continuous variables (mean, standard deviation, median, IQR, number of observations, minimum, maximum and 95% confidence intervals) and discrete variables (percentage, count/sample and 95% confidence intervals). Confidence intervals (95%) for the difference between means will be used to compare groups. For proportions, 95% confidence intervals will be reported. For time-to-event analyses, all subjects not having an event or lost to follow-up will be censored at the time of the last documented follow-up visit.

Explorative analyses may include but will not be limited to the study endpoints. A variety of methods may be utilized to assess associations between the likelihood of each of the study endpoints and the patient and procedural characteristics.

Methods to model multivariate associations may include but are not limited to the following:

- 1. Univariate analysis of individual predictors, and subsequent construction of multivariate logistic regression models incorporating all significant univariate predictors.
- 2. Parsimonious multivariate logistic regression models constructed through stepwise selection algorithm.
- 3. Classification and regression tree models.

4.3 Control of Systematic Error/Bias

Selection of subjects will be made from the Investigator's usual subject load. Nonvalvular AF patients who require treatment for potential thrombus formation and meet the inclusion/exclusion criteria will undergo an echocardiographic examination (via TTE and TEE) to further evaluate other Echocardiographic Exclusion Criteria to minimize the selection bias.

If the baseline TTE and TEE confirms the subject does not meet any of the Echocardiographic Exclusion Criteria, the subject is eligible for study enrollment. If the baseline TEE confirms the presence of any intracardiac thrombus, the subject may be treated with anticoagulation therapy. After an appropriate period of time, these subjects will return for another baseline TEE to assess evidence of intracardiac thrombus and other baseline criteria. Only when the thrombus has completely resolved is the subject eligible for study enrollment.

In addition, screen failures who experience an AE associated with diagnostic testing or medication changes in preparation for device implantation will also be followed for 45 days from AE onset or until the AE is resolved.

4.4 Number of Subjects per Investigative Site

No limitations on the maximum number of enrolled subjects for each investigative site will be set.

5 ADDITIONAL DATA ANALYSES

The analyses described in this section will be performed after the corresponding primary or secondary endpoint analysis has been completed. No adjustments for multiple comparisons will be made. Additional analyses will be performed as appropriate.

5.1 Justification of Pooling

Poolability across investigational center will be assessed for all primary and secondary endpoints. Poolability of the primary effectiveness and safety endpoints across investigational center will be assessed by adding center into a logistic regression model as a random effect. Centers will be deemed to be heterogeneous if the variance of the random center effect is found to be significantly different from zero using a significance level of 0.15. Regardless of the results of the poolability analyses, results by investigational center will be provided for each primary and secondary endpoint.

5.2 Interim Analyses

No Interim analysis is planned for the study.

5.3 Subgroup Analyses

No subgroup analysis is planned for the study.

5.4 Multivariable Analyses

Multivariate analyses may be utilized in order to assess associations between the likelihood of outcomes and the pre-specified patient and procedural characteristics outlines in **Error! Reference source not found.**1.

Table 5-1: Covariates of Interest

| Age (< 80 years vs. \geq 80 years) |
|--|
| Sex (Female vs. Male) |
| Type of AF (paroxysmal; persistent; permanent) |
| Previous Stroke/TIA |
| Previous major bleeding event (intracranial/extracranial) |
| Bleeding risk (HAS-BLED $< 3 \text{ vs} \ge 3$) |
| Stroke risk (CHADS ₂ $<$ 3 vs \geq 3) |
| Stroke risk (CHA ₂ DS ₂ -VASc < 5 vs ≥ 5) |
| Type of anticoagulation therapy (Warfarin; NOACs; antiplatelet) |
| Multiple concomitant procedures vs watchman implant only |

Methods to model multivariate associations may include but are not limited to the following:

Form/Template 90702621 Rev/Ver AF, Boston Scientific WATCHMAN FLX™ HK Study, SAP, 92820808, Rev/Ver AA Page 12 of 14

- (1) Univariate analysis of individual predictors, and subsequent construction of multivariate logistic regression models incorporating all significant univariate predictors.
- (2) Parsimonious multivariate logistic regression models constructed through stepwise selection algorithm.
- (3) Classification and regression tree models.

5.5 Other Analyses

Baseline and procedural characteristics, patient and device dispositions, antiplatelet and anticoagulants medication usage, additional echocardiographic measurements, device deficiency, site-reported adverse events, protocol deviations will be reported. Data and outcome variables will be summarized using descriptive statistics for continuous variables (mean, standard deviation, median, IQR, number of observations, minimum, maximum and 95% confidence intervals as applicable) and discrete variables (percentage, count/sample and 95% confidence intervals).

5.6 Changes to Planned Analyses

Any changes to the planned statistical will be documented in a Statistical Analysis Plan. Changes from the planned statistical methods will be documented in the clinical study report along with a reason for the deviation.

6 VALIDATION

All clinical data reports generated per this plan will be validated per 90702587, Global WI: Clinical Data Reporting Validation.

7 PROGRAMMING CONSIDERATIONS

7.1 Statistical Analysis Software

All statistical analyses will be performed using the SAS System software, version 9.4 or later (Copyright[©] 2000 SAS Institute Inc., [name]. All rights reserved).

All statistical analyses will be conducted according to applicable Standard Operating Procedures, Work Instructions, and the study-specific Statistical Analysis Plan.

7.2 Subject Days (last follow-up days)

Each subject will be followed for 12 months after the implant. In case of premature termination of the study, data collection will stop accordingly. As this is an observational study, subjects will be managed according to standard of care as per centers practice following termination/completion of the study.

- 1. The date on End of Study form (subject exits the study due to death, withdrawal, lost to follow up, or completed study).
- 2. If subject didn't exit the study and has a corresponding follow-up visit (eg: procedure date, discharge date, adverse event date, site-reported echo date, follow-up visit date, hospitalization date), then visit date is used.

3. The procedure date is considered as the starting point of a patient for any of the analysis specified in this statistical analysis plan.

7.3 Clinical Event Rates

- 1. Rates at Procedure: the proportion of subjects who experience an event on the same day as the index procedure out of all subjects.
- 2. Rates through Discharge/7 days Post-procedure: the proportion of subjects who experience an event through discharge or 7 days post-procedure (whichever comes later) out of all subjects.
- 3. Rates at 30-100 Days Post procedure: the proportion of subjects who experience an event through 30-100 days post-procedure out of the subjects who have either had an event within 30-100 days post-procedure or who were event-free with last follow-up at least 30 days post-procedure.
- 4. Rates through 1-Year Post procedure: the proportion of subjects who experience an event through 365 days post-procedure out of the subjects who have either had an event within 395 days post-procedure or who were event-free with last followup at least 335 days post-procedure.

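### SAP 7.3 item 3: the 30-100 day event rate counts events from day 0 in its numerator, but read literally its denominator omits subjects whose only event falls on days 0-29

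*SAP*

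**What the plan says.** SAP 7.3 item 3 has three parts:

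- Numerator: "the proportion of subjects who experience an event through 30-100 days post-procedure".
- Denominator, event part: "out of the subjects who have either had an event within 30-100 days post-procedure".
- Denominator, event-free part: those "who were event-free with last follow-up at least 30 days post-procedure".

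SAP 7.2 sets the clock: "The procedure date is considered as the starting point of a patient for any of the analysis" in the SAP.

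SAP 3.5 says where the rate is used. The primary endpoint report is to give "Additional endpoints and other major clinical events, including the occurrence of below events at 30-100 days follow-up". The list is stroke, TIA, cardiovascular death, systemic embolism, device embolization, device thrombus, serious pericardial effusion and major bleeding. SAP 3.4 asks for a percentage, a count over sample size and a 95% confidence interval for each proportion.

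The neighbouring items in SAP 7.3 are built differently. Item 2 counts events "through discharge or 7 days post-procedure (whichever comes later) out of all subjects". Item 4, the one-year rate, forms the event part of its denominator "out of the subjects who have either had an event within 395 days post-procedure". No other section of either document says how the 30-100 day rate is formed.

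**The concern.** The numerator runs up to the first follow-up from the procedure, so an event on day 2 counts. The denominator's event clause carries a lower bound of 30 days, and the other clause requires no event at all. A subject whose only event is on day 2 satisfies neither, so the rule as written puts subjects above the line who are not below it.

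A programmer has to settle this in one of three ways: follow the text, extend the denominator back to day 0, or cut the numerator down to days 30-100. The last two are both coherent, but they answer different questions.

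Early events are plausible for several listed items, because Protocol 11.5 collects effusion, tamponade, bleeding, stroke and systemic embolism as peri-procedural complications. SAP 7.5 also sets a wholly missing onset date to the procedure date, which puts that event on day 0. The primary safety endpoint does not fully cover this ground: it excludes effusions drained by catheter and embolized devices retrieved by snare, and major bleeding is not a component.

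**Working it through.** **The plan's own figures.** The SAP gives no figure for the 30-100 day rate. Its only rate table is the exact interval for 0 to 5 events among 50 subjects (SAP 3.1). Clopper-Pearson limits reproduce all six rows to one decimal, for example 3/50 = 6% (1.3-16.5%). The table is not in dispute, and the same method is used below.

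**Inputs.** Day 0 is the procedure date (SAP 7.2). For the number of subjects N, 40 is taken from SAP 4.1 ("It is estimated that both primary effectiveness analysis and primary safety analysis dataset will include at least 40 subjects") and 50 is the enrollment ceiling. SAP 4.1 leaves the data set for the additional analyses open, so using 40 here is an assumption. The event and loss counts are also assumptions, since the documents give none.

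**Notation, for one type of event.**

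- e = subjects whose only event is on days 0-29
- l = subjects with an event on days 30-100
- w = event-free subjects last seen before day 30
- f = N - e - l - w, the event-free subjects last seen at day 30 or later

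**Three readings.**

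- Literal: (e + l)/(l + f)
- Cumulative in both places: (e + l)/(e + l + f)
- Days 30-100 in both places: l/(l + f)

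| N, e, l, w | Literal | Cumulative (exact 95% CI) | Days 30-100 only (exact 95% CI) |
|---|---|---|---|
| 40, 0, 1, 0 | 1/40 = 2.5% | 1/40 = 2.5% (0.1-13.2%) | 1/40 = 2.5% (0.1-13.2%) |
| 40, 1, 0, 0 | 1/39 = 2.6% | 1/40 = 2.5% (0.1-13.2%) | 0/39 = 0% (0-9.0%) |
| 40, 3, 0, 0 | 3/37 = 8.1% | 3/40 = 7.5% (1.6-20.4%) | 0/37 = 0% (0-9.5%) |
| 40, 3, 1, 0 | 4/37 = 10.8% | 4/40 = 10.0% (2.8-23.7%) | 1/37 = 2.7% (0.1-14.2%) |
| 40, 3, 1, 2 | 4/35 = 11.4% | 4/38 = 10.5% (2.9-24.8%) | 1/35 = 2.9% (0.1-14.9%) |
| 40, 5, 0, 0 | 5/35 = 14.3% | 5/40 = 12.5% (4.2-26.8%) | 0/35 = 0% (0-10.0%) |
| 50, 3, 0, 0 | 3/47 = 6.4% | 3/50 = 6.0% (1.3-16.5%) | 0/47 = 0% (0-7.5%) |

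No interval is shown for the literal column when e > 0. Its numerator is not contained in its denominator, so a binomial interval does not apply.

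**What the table shows.** The literal rule exceeds the cumulative rate by the factor (e + l + f)/(l + f). At N = 40 with nobody lost, the excess runs from about 0.1 point with one early event (2.56% against 2.50%) to 1.8 points with five (14.29% against 12.50%). The gap between the two coherent readings is larger: 7.5 points for three early events and no late one, and 10.0 - 2.7 = 7.3 points when one late event is added.

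**Items 2 and 4.** Item 2 divides by all subjects, so nobody can be missing from its denominator. In item 4 the event clause has an upper limit and no lower one, so an event on day 2 enters both parts. Only item 3 puts a two-ended range in that clause. The different day limits within item 4 are a separate matter.

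**The case against.** The best defence is that item 3 has one sensible meaning. The range of 30 to 100 days is the label of the First Follow-up visit, item 4 follows the same template with time plainly counted from the procedure, and SAP 7.2 fixes that origin for every analysis. A proportion must also contain its own numerator. On this view item 3 simply means events up to First Follow-up, and 3/40 is the answer. That is probably what was intended. But item 4's clause has no lower bound and item 3's does, and nowhere does the SAP say that the bound should be ignored.

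The defence is right about size and reach. The excess under the literal rule is small beside intervals roughly 19 points wide (1.6-20.4%), and these rates are descriptive, with no hypothesis test.

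A reader might infer three stronger things, and the documents support none of them:

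- **That the primary endpoint results are wrong.** The primary safety window matches item 2, which uses all subjects. Primary effectiveness is an imaging finding in implanted subjects who completed First Follow-up (SAP 4.1).
- **That peri-procedural events would vanish from reporting.** Even if the rate were confined to days 30-100, site-reported adverse events are summarized (SAP 5.5) and the 12-month rates count from day 0. Items 1 and 2 also define early rates, although SAP 3.5 does not call for those rates for the listed events in the first report.
- **That early events are the majority.** The documents give no timing of events for this device, and the list includes device thrombus, TIA, major bleeding and cardiovascular death, which are not confined to the first 29 days.

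**Conclusion.** The point holds as an internal inconsistency in one definition. Applied as written, item 3 does not give a proportion whenever a subject's only event falls on days 0-29. It concerns only the eight descriptive event types listed in SAP 3.5 for the 30-100 day report.

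With 40 subjects and one to five early events, the literal rule overstates the cumulative rate by about 0.1 to 1.8 percentage points. The more serious consequence is that the text does not settle between a cumulative rate and a day 30-100 rate: in the three-event illustration these are 7.5% and 0%. All the sizes rest on assumed counts. If no early events occur, the readings coincide and nothing changes.

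It should be corrected before the first report is programmed, but it is not a threat to the study's main results.

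**What to change.** Use one interval in both places, counted from the procedure as in item 4:

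- Numerator: subjects with an event from day 0 through day 100 after the procedure.
- Denominator: those same subjects, plus subjects with no event through day 100 whose last follow-up is at day 30 or later.

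A fixed end at day 100 is preferable to ending at each subject's own visit. A visit-based end would leave unclear how to treat an event after an early visit but before day 100, and would give no end date for a subject without the visit.

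If a day 30-100 window rate is what the sponsor wants, the SAP should say so and restrict the numerator to those days.

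The cost is one sentence in the SAP, with no new data and no change to the primary endpoints. One limit carries over from the present rule: an event-free subject last seen at day 35, say, counts fully although not observed to day 100.

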| Device Sizes | WATCHMAN FLX is available in 20, 24, 27, 31, and 35mm models to fit left atrial appendage ostia widths ranging from $14.0 - 31.5$ mm. |
| Indication(s) for Use | WATCHMAN FLX is intended to prevent thrombus embolization from the left atrial appendage and reduce the risk of life-threatening bleeding events in patients with non-valvular atrial fibrillation who are eligible for anticoagulation therapy or who have a contraindication to anticoagulation therapy. |
| Population | Patients with non-valvular atrial fibrillation in Hong Kong area. |
| Enrolment | Up to 50 patients at up to 5 investigational centres in Hong Kong will be enrolled in the study. |
| Study Duration | Enrollment is expected to be completed in approximately 12 months and each subject is expected to be followed for approximately 12 months with primary endpoints collected at First Follow-up (30-100 days); therefore, the total study duration is estimated to be approximately 24 months. The study duration for each subject is expected to be approximately 12 months. |
| Patient follow-up | Each subject will be followed for a period of one year after implantation according to the device labelling. |
| | Study procedures and follow-up visits will occur as follows: Enrolment Visit WATCHMAN FLX implant First Follow Up (FU) (30 to 100 days) 12-month FU (365 ±30 days) |

| | 1450 5 01 1 1 |
|--------------------|---|
| Objectives | The primary objective of this study is to observe the safety and effectiveness of the WATCHMAN FLX [™] Left Atrial Appendage Closure (LAAC) Device for subjects with non-valvular atrial fibrillation to reduce the risk of stroke in Hong Kong area. |
| | Primary Effectiveness Endpoint: The occurrence of non-effective LAA closure defined as any peri- device flow > 5mm demonstrated by TEE/CT/MRI at First Follow- up. |

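### The SAP's 30-100 day clinical event rate has no single time horizon, so it moves with the timing of the First Follow-up visit

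*SAP*

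**What the plan says.** SAP 7.3 defines four clinical event rates. Item 3 is "the proportion of subjects who experience an event through 30-100 days post-procedure". Its denominator has two parts. One takes in subjects with an event in the window: "out of the subjects who have either had an event within 30-100 days post-procedure". The other takes in subjects counted as "event-free with last follow-up at least 30 days post-procedure". The neighbouring items do name a horizon: item 2 uses discharge or 7 days, and item 4 counts events to day 365 and asks event-free subjects for at least 335 days.

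SAP 3.5 gives item 3 its use. The primary endpoint report will contain "Additional endpoints and other major clinical events, including the occurrence of below events at 30-100 days follow-up": stroke, TIA, cardiovascular death, systemic embolism, device embolization, device thrombus, serious pericardial effusion and major bleeding.

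SAP 7.2 sets the last follow-up date. A subject who has left the study takes the End of Study date. For one still in the study with a qualifying visit or event, "then visit date is used". SAP 3.4, 4.2 and 7.5 mention censoring only for time-to-event analyses that are not specified, and none of them ties it to the item 3 rates.

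**The concern.** The numerator can look as far as day 100, while the denominator certifies a subject as complete from day 30. A subject last seen event-free on day 30 and another last seen event-free on day 100 carry the same weight, although the first was observed for 30% of the longest period. Item 4 is much tighter: 335 of 365 days, or 92%.

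The result is a proportion at no defined time. Two centres with identical risk could report different figures because one books the visit at six weeks and the other at three months. Protocol section 6 and SAP section 2 foresee using the data in product registration to argue that ethnic difference matters little, with a US study as the reference. A rate whose time point is set by clinic scheduling is a weak basis for that comparison.

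**Working it through.** **The plan's own figures.** The SAP states no 30-100 day rate. Its only computable figures are the exact 95% intervals for 0 to 5 events in 50 (SAP 3.1). Clopper-Pearson limits reproduce all six rows to one decimal; for 0 events the upper limit is 1 − 0.025^(1/50) = 7.1%. They do not bear on the horizon.

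**Inputs from the documents.** First Follow-up window, days 30 to 100; next scheduled contact, 365 ± 30 days; up to 50 subjects enrolled, at least 40 expected in the primary analysis sets; enrollment over about 12 months.

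**Assumptions.** The documents give neither event rates for this window nor visit dates. Take a true 100-day risk p = 5%, and for the main table no capture of events between the last visit and day 100.

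**Expected item 3 rate when the last visit is on day t, with no loss before day 30.**

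- Constant hazard: 1 − (1 − p)^(t/100). At t = 30: 1 − 0.95^0.30 = 1.5%.
- Share s of the risk in days 0-7, the rest even over days 7-100: p × [s + (1 − s)(t − 7)/93]. At s = 0.9, t = 30: 5% × (0.9 + 0.1 × 23/93) = 4.6%.

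| Timing of risk | All seen day 30 | All seen day 45 | Even over 30-100 | All seen day 100 |
|---|---|---|---|---|
| Constant hazard | 1.5% | 2.3% | 3.3% | 5.0% |
| 70% in days 0-7 | 3.9% | 4.1% | 4.4% | 5.0% |
| 90% in days 0-7 | 4.6% | 4.7% | 4.8% | 5.0% |

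As a ratio to the true risk, the first row runs from 1.5/5.0 = 0.3 to 1.0 and the last from 4.6/5.0 = 0.92 to 1.0. Under constant hazard, a true risk of 3% gives 0.9% to 3.0%, and 10% gives 3.1% to 10.0%.

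**Capture of events after the visit.** Constant hazard, visits even over the window, 80% captured: 3.27% + 0.8 × (5.0% − 3.27%) = 4.65%. With full capture, 5.0%.

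**Loss before day 30.** Event-free subjects lost before day 30 leave the denominator, while early events stay in. Take 90% of the risk in days 0-7, visits even over the window, and a fraction d lost uniformly over days 0-30. The mean risk to the visit is then 4.81%, and the mean risk to the loss date is 4.02%. The rate is [(1 − d) × 4.81% + d × 4.02%] / [(1 − d) + d × 0.0402]. At d = 5% this is 4.77%/0.952 = 5.0%; at d = 10% it is 4.73%/0.904 = 5.2%. Under constant hazard the same loss hardly matters (3.3% to 3.4%).

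**Small invented example, n = 40.** Events on days 5 and 80; 20 subjects last seen event-free on day 35 and 18 on day 95. Item 3 gives 2/40 = 5.0%. Kaplan-Meier after day 80 gives 1 − (39/40)(18/19) = 7.6%.

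**A related wording problem.** Read literally, the denominator admits events only within days 30-100, so an event before day 30 would be counted above the line but not below it. Two early events among 40 would give 2/38 = 5.3% instead of 2/40 = 5.0%.

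**The case against.** The strongest reply is that the SAP never promises a 100-day risk. SAP 3.5 ties these events to the follow-up visit, and a natural reading of item 3 is occurrence through the First Follow-up. On that reading nothing is understated; the rate is only poorly labelled. This stands as far as it goes, but it concedes that the time point varies by subject, and the SAP does not ask for the distribution of follow-up days.

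Second, the large ratios need assumptions that the documents make doubtful for some events. Protocol 4.2 describes pericardial effusion with tamponade and device embolization as procedural complications, so their risk is probably early. Protocol Table 8 requires serious events to be reported within 24 hours of site awareness through the end of the study, and SAP 7.2 accepts event, echo and hospitalization dates as follow-up. For ischemic stroke, the 2.3 per 100 patient-years cited from the second pivotal study implies 50 × 0.023 × 100/365 = 0.32 expected events by day 100 and 0.09 by day 30, so about 0.2 of one event could be missed. This also stands, with a limit: reporting depends on the site learning of the event, and after the First Follow-up no contact is scheduled until day 335 at the earliest. If accrual is even over 365 days and the data are cut 100 days after the last implant (both assumptions), only (465 − 395)/365 = 19% to (465 − 335)/365 = 36% of subjects would have reached the 12-month visit.

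Third, with 40 to 50 subjects one event moves a rate by 2.5 to 2 percentage points, so sampling error may exceed the bias. True, but the undefined horizon is a separate fault that costs little to remove.

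**Conclusion.** The point holds as a defect of definition. Item 3 mixes horizons, and the additional clinical event rates in the primary endpoint report depend on visit timing. The size is conditional on the assumed timing and capture of events, as the table shows, and the documents do not allow it to be fixed more closely.

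Four stronger readings are tempting and are not supported:

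- *The primary results are distorted.* They are not. Primary safety ends at 7 days or discharge, primary effectiveness is imaging at the visit, and the secondary endpoint is at 12 months.
- *The rates are always too low.* Low is the usual direction when they are read as 100-day risks, but early loss of event-free subjects can cancel or reverse it.
- *The shortfall is known to be large.* The factor of 0.3 needs a constant hazard, every visit at day 30 and no capture afterwards.
- *The figures will shift in the 12-month report.* SAP 3.5 does not list the 30-100 day clinical event rates there; it lists the same events at 12-month follow-up.

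This should be corrected before the primary endpoint report is produced. It is not a threat to the study's main results.

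**What to change.** Replace item 3 of SAP 7.3 with two summaries:

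1. The proportion with an event through day 30. Keep every event from day 0 to day 30 in both numerator and denominator, and add all subjects known to be event-free to day 30. State how many event-free subjects were lost earlier.
2. A Kaplan-Meier or cumulative incidence curve, with event-free subjects censored at last documented contact and numbers at risk shown. Read it at a later fixed day only where enough subjects remain at risk.

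If a rate at the visit is kept, label it as running through First Follow-up and give the median and range of follow-up days. Device thrombus is found on imaging, so report it as a proportion of subjects imaged at First Follow-up, with the range of imaging days.

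The cost is SAP wording and a little more programming in the software already named. The interval may become much wider towards day 100 if many visits fall early. If every subject were last seen by day 45, nobody would be at risk at day 100 and no estimate there should be given.
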